6. The PACT team and patient will use the shared understanding of adaptive challenges to find creative ways to do the adaptive work to reduce the impact of symptoms, function, and physical health.
7. The patient and PACT team will establish Smart, Measurable, actionable, Realistic, and Timed (SMART) goals, which are reassessed twice weekly and located on the patient's dry erase board in their hospital room. The adaptive work can be introduced in small, achievable goals to optimally engage in PACT.

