5.3 Description of Assessments and Questionnaires

Assessment Tool	Discipline	Indication
European Organization for Research and Treatment of Cancer QLQ-C30	PI or Research Assistant	Self-report QOL: functional scale & symptom scale
PRO version of the Common Terminology for Adverse Events (PRO-CTCAE)	PI or PACT RN	19 items** (diarrhea, chills, heartburn, nausea, appetite, mouth sores, vomiting, constipation, cough, rash, shortness of breath, fatigue, anxiety, sadness, nothing will cheer me up, pain, insomnia, concentration, and memory)
Activity Measure in Post-Acute Care (AM-PAC)	OT & PT	Guides discharge planning; guides resource utilization; provides insight re: patient mobility
Karnofsky Performance Scale (KPS)	PI or Research Assistant	Classified participants' functional impairment
Possibilities for activity Scale (PACTS)	PI or Research Assistant	Assessing self-efficacy and motivation of performing meaningful activity

Timed Up and Go~10 feet (3 meters)	PT	Assesses patient mobility, balance and fall risk
BERG Balance	PT	Falls Risk
Muscle Strength	OT	Prognostic & Predictive Marker, Handheld Dynamometry
Modified Canadian Occupational Performance Measure (COPM)	OT	Self-care, leisure, and productivity outcomes; goal attainment scale
Performance Assessment of Self-care Skills (PASS)	OT	Ability to perform daily tasks
Clock Drawing	OT	Assess cognitive abilities
Demographics and Clinical Characteristics	PI or Research Assistant	Demographic: date of birth/age, sex, race/ethnicity, insurance, education, income, marital/partner status, number of people in the household, employment status, insurance type, falls in last 6 months Clinical: type of acute leukemia, white blood cell, hemoglobin, hematocrit, platelets, lactate dehydrogenase, neutrophil count, cytogenetics and blast percentage, height and weight, comorbidity, and treatment type(s)
Care Transitions Measure (CTM)	PI or Research Assistant	Assesses readiness for discharge
Patient Activation Measure (PAM)	PI or Research Assistant	Assesses self-management
Preparedness for Caregiving Scale FACT-Leu Additional Concern subscale	PI or Research Assistant PI or Research Assistant	Assesses preparedness for caregiving Assess disease burden

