8.0 TIME AND EVENTS TABLE

Table 5. Measures

Variable Measured	Measure Description and Reliability	Baseline cycles 1 & 2 (7 days prior or within 3 days of infusion initiation)	Symptom and QOL BOTH GROUPS (About days 1-60)	HMA or low-dose cytarabine completion at cycle 1 & 2 (within 2 days or up to 7 days after the end of infusion)	Post-discharge, 2x week assessments Monday & Thursday INTERVENTION ONLY days 8-30	Before cycle 4 (About day 90)	Data Collector
Demographic and clinical variables	Age, sex, race/ethnicity, insurance, education, income, employment status, marital/partner status, number of people in the household. Treatment type, comorbidities, remission status, blood test results, height and weight.	X			Continuously monitor clinical characteristic, ex: blood result, remission status		Research Assistant
Health Care Utilization	Number and reasons for: emergency department visits, rehospitalizations Length of hospital			Electronic chart abstraction and self-report			Research Assistant
Quality of Life							
QOL	EORTC QLQ-C30 ³⁰ , $\alpha = .89$ (5 functional scales, global health status/QOL scale, cognition, financial impact)	X	X (baseline of cycle 3)			X	Research Assistant
Symptoms							
AML symptoms	PRO-CTCAE 19 items ⁴² (diarrhea, chills, heartburn, nausea, appetite, mouth sores, vomiting, constipation, cough, rash, shortness of breath, fatigue, anxiety, sadness*, nothing will cheer me up, pain, insomnia, concentration, and memory)	X	X	X	X	X	PACT RN
Disease burden	FACT-Leu Additional Concern subscale	X				X	Research Assistant
Function							
Participation in Meaningful Activity	Possibilities for Activity Scale (PActS) ³⁴ - 12 items stratified $\alpha = .77$ – internal consistency .91 - .89	X				X	Research Assistant
Performance Status	Clinician reported Karnofsky Performance Scale ³⁷ - 1 item for clinician; $r = .89$	X		X		X	Research Assistant
Self-care	PASS- Performance Rate Assessment of Self-Care Skills	X					PACT OT
Grip Strength	Hand grip strength	X					PACT OT
Balance	Berg balance test	X					PACT PT
Mobility	Timed Up and Go (3 meter)	X					PACT PT
Function	Activity Measure for Post-Acute Care (AM-PAC) "6 clicks" - 6 items for OT; 6 items for PT; $\alpha = .92 - .94$	X					PACT OT and PT
Cognition abilities	Clock Drawing Assessment	X					PACT OT
Readiness for Discharge and Self-Management							
Readiness for Discharge	Care Transitions Measure ⁴³ , 15 items, $\alpha = .93$			X			PACT RN

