Self-management	Patient Activation Measure ⁴⁴ , 13 items, $\alpha = .87$			X			PACT RN
Preparedness for Caregiving	Preparedness for Caregiving Scale			X			PACT RN
Other							
Patient and Caregiver Interview				X			Research Assistant

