11.4 Data Management and Monitoring/Auditing

All study data will be collected, managed, and stored via PRO Core Survey System using a unique patient identifier. PRO Core is a secure platform for collecting data via web-enabled devices. It facilitates study management through patient tracking reports and email reminders to project staff. It allows symptoms to be tracked from baseline up to 24 weeks post discharge. Data are stored in a secure database managed by the Information Technology Science (ITS) Research Computing group at UNC.

As an investigator-initiated study, this trial may be audited by the Lineberger Cancer Center audit committee.

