13.2.14 Care Transitions Measure

ID: _____

CARE TRANSITIONS MEASURE (CTM-15)

Patient Name: _____ Date: _____

Who completed interview? Patient Caregiver

The first few statements are about the time you were in the hospital . . .

1. Before I left the hospital, the staff and I agreed about clear health goals for me and how these would be reached.

Strongly Disagree	Disagree	Agree	Strongly Agree	Don't Know/ Don't Remember/ Not Applicable
----------------------	----------	-------	-------------------	--

2. The hospital staff took my preferences and those of my family or caregiver into account in deciding *what* my health care needs would be when I left the hospital.

Strongly Disagree	Disagree	Agree	Strongly Agree	Don't Know/ Don't Remember/ Not Applicable
----------------------	----------	-------	-------------------	--

3. The hospital staff took my preferences and those of my family or caregiver into account in deciding *where* my health care needs would be met when I left the hospital.

Strongly Disagree	Disagree	Agree	Strongly Agree	Don't Know/ Don't Remember/ Not Applicable
----------------------	----------	-------	-------------------	--

The next set of statements is about when you were preparing to leave the hospital . . .

4. When I left the hospital, I had all the information I needed to be able to take care of myself.

Strongly Disagree	Disagree	Agree	Strongly Agree	Don't Know/ Don't Remember/ Not Applicable
----------------------	----------	-------	-------------------	--

5. When I left the hospital, I clearly understood how to manage my health.

Strongly Disagree	Disagree	Agree	Strongly Agree	Don't Know/ Don't Remember/ Not Applicable
----------------------	----------	-------	-------------------	--

ID: _____

6. When I left the hospital, I clearly understood the warning signs and symptoms I should watch for to monitor my health condition.

Strongly Disagree	Disagree	Agree	Strongly Agree	Don't Know/ Don't Remember/ Not Applicable
------------------------------	-----------------	--------------	---------------------------	---

7. When I left the hospital, I had a readable and easily understood written plan that described how all of my health care needs were going to be met.

Strongly Disagree	Disagree	Agree	Strongly Agree	Don't Know/ Don't Remember/ Not Applicable
------------------------------	-----------------	--------------	---------------------------	---

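### Section 5.3 and Table 5 name different collectors for the readiness, activation and caregiver-preparedness scales; if the PACT RN administers them, the contrast can be biased toward PACT

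*Combined protocol and SAP*

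**What the plan says.** Two tables assign the same three instruments to different people.

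- **Section 5.3.** The rows for "Care Transitions Measure (CTM" and "Patient Activation Measure (PAM" both carry the PI or a research assistant. The caregiver scale shares a merged row with the FACT-Leu subscale, whose collector cell reads "PI or Research Assistant PI or Research Assistant". Both halves are the same, so the merge leaves no doubt about the assignment.
- **Section 8.0, Table 5.** Under "Readiness for Discharge and Self-Management", the CTM, the PAM and the "Preparedness for Caregiving Scale" all have the PACT RN as data collector. Each is marked once, in the column for completion of the infusions in cycles 1 and 2. None has a baseline mark.

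The PACT RN is an interventionist. Section 2.0 has RNs, OTs and PTs deliver PACT. Table 1 has the RN lead the shared-understanding work and telephone patients twice a week. Section 1.3 adds: "The patient and PACT team will establish Smart, Measurable, actionable, Realistic, and Timed (SMART) goals".

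The primary objective (Section 3.1) includes readiness for discharge as reported afterwards by patients and caregivers. Section 11.4 says of the data system: "PRO Core is a secure platform for collecting data via web-enabled devices".

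**The concern.** Site staff cannot follow both tables, so who collects these scales would be settled informally and might differ between patients or between the two phases of the study.

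The Table 5 version also carries a risk of its own. CTM item 1 reads: "Before I left the hospital, the staff and I agreed about clear health goals for me and how these would be reached". In the PACT group, the person receiving the answer would belong to the team that set those goals with the patient. Respondents tend to answer kindly to someone who has helped them, and self-report does not protect against that. If the tendency is stronger in one group, it enters the group difference directly.

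Section 10.3 plans no formal testing. The effect estimates are the product, and they are meant to inform a later grant application. A systematic shift would be carried into that planning without showing in the confidence interval.

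**Working it through.** No arithmetic decides this point; it rests on comparing the entries.

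| Instrument | Collector, Section 5.3 | Collector, Table 5 | What the form asks |
|---|---|---|---|
| CTM | PI or research assistant | PACT RN | Items 1 to 3 rate how staff handled goals and preferences; the others rate the patient's understanding and plans |
| PAM | PI or research assistant | PACT RN | The patient's own beliefs and confidence |
| Preparedness for Caregiving | PI or research assistant | PACT RN | The caregiver's own preparedness |

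1. **Is the conflict real?** Yes, for all three. No text elsewhere reconciles the tables or names a separate collector for controls.

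2. **Is the PACT RN close to the content measured?** Yes. By infusion completion the RN has worked with the PACT patient daily through the first week (Section 2.0, Table 1) and taken part in goal-setting. The scales are marked only after that contact has begun.

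3. **Does the relationship differ between groups?** Probably, in degree. Controls receive usual care, and the ten of them finish before the PACT group starts (Section 2.0). They have no joint goal-setting and no twice-weekly calls. They may still meet the same nurse, because Table 5 also has the PACT RN collect PRO-CTCAE in a column covering both groups.

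4. **Can the analysis absorb a shift?** Not as scheduled. The ANCOVA in Section 10.3 adjusts for the baseline value, and these scales have no baseline mark. A baseline would not remove a bias that arises after the relationship forms in any case.

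5. **Does the precision figure help?** No. Section 10.2 states a 95% half-width of .9SD for QOL with 10 per group. This reproduces: 1.96 × √(2/10) = 0.88 SD with the normal quantile, and 2.10 × √(2/10) = 0.94 SD with t on 18 df. It describes random error, was stated for QOL and not for these scales, and does not change with who collects the data.

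6. **Would adopting Section 5.3 unchanged suffice?** No. It permits the PI, who helps train the PACT team and observes and records 20% of its checklist sessions (Section 1.5, training and fidelity text).

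**The case against.** The conflict between the tables is not open to dispute. The bias argument has limits, and most of the case against it stands.

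- **One group only.** A reader might infer that controls have no relationship with the collector, so that courtesy bias acts in the PACT group alone. The documents do not establish this. On the Table 5 reading, controls may see the PACT RN repeatedly for daily PRO-CTCAE (Section 5.3 says the PI or PACT RN), and the PACT nurses are existing site employees. What can be said is that the working relationship is closer in the PACT group.
- **All three scales equally.** The staff-rating mechanism fits the CTM. The PAM and the caregiver scale ask respondents about themselves, and the PAM is circled by the patient on a form that itself cautions against answering to please others. Some courtesy effect is possible there, but the case is weaker.
- **All three in the primary objective.** Readiness for discharge is named there. Activation is not, and caregiver preparedness is covered at most by inference. The primary endpoints in Section 3.4 are feasibility and adherence.
- **Bias as an established fact.** Mode of administration is not specified. If respondents complete the forms alone in PRO Core, the nurse may do no more than hand over a device. Against that, the CTM form asks who completed the interview, which suggests interviewer administration for that scale.
- **Low stakes.** The comparison is for estimation only. That lowers the stakes but does not remove them, because the estimates feed later planning.

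**Conclusion.** The contradiction is certain and covers all three instruments. The bias is conditional: if the PACT RN administers the forms, the contrast can be biased toward PACT. That rests on two assumptions: that the nurse's presence influences answers, and that the closer relationship in the PACT group makes the influence stronger there. Both are plausible, but neither is shown in the documents.

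The risk is clearest for the CTM and smaller for the PAM and the caregiver scale. Its size is unknown. Any shift expressed in SD units would be invented, and setting one against the .9SD half-width would compare bias with random error on a different outcome. A reader might also infer that Section 5.3 already provides an independent collector. It does not, because it allows the PI.

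This is worth correcting before enrolment; it does not invalidate the design.

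**What to change.** - In Table 5, change the collector for the CTM, the PAM and the caregiver scale to a research assistant who takes no part in delivering PACT. Alternatively, specify unassisted self-completion in PRO Core.
- State the mode of administration, and use the same one in both groups.
- Amend Section 5.3 to match by removing the PI as an alternative collector for these three scales.

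The cost is two table edits and a small shift of work to the research assistant, who already conducts the patient and caregiver interview in the same Table 5 column. No new visit or post is needed. The change does not touch bias from the sequential, unblinded groups, which should still be acknowledged when these contrasts are reported.

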9.0 EXPECTED RISKS/UNANTICIPATED PROBLEMS/SAFETY MONITORING

9.1 Expected Risks

To minimize the risk of infections, since the leukemia population becomes very susceptible to infections during treatment, all members of the research team will follow standard neutropenic and protective precautions. Also, the research team will attempt to isolate each piece of exercise equipment to a particular patient room. In case a particular piece of equipment needs to be moved from one room to another, the equipment will be disinfected following standard protocols already in place on the oncology floors. During the study, no equipment will leave the oncology floors. If a research team member is ill, he or she will not be assigned to see any patients during the illness. Also, due to the stringent criteria for participation in the study, only patients deemed capable by their oncologists will be enrolled in the study.

9.1.1 Physical Risks

Timed walk testing requires physical exertion and may result in musculoskeletal injury. Patients with contraindications to physical activity will not be asked to participate in walking. Previously published data¹⁶ have demonstrated that exercise testing in the target patient population is feasible and safe. The research team will take all appropriate precautions to prevent injury. In the unlikely event of injury during the fitness assessments, such as muscle distensions and joint trauma, medical professionals on the research team will provide the appropriate care.

9.1.2 Emotional Risks

Some questions in the patient questionnaires could create emotional distress or confusion. Patients will be instructed that the questionnaires are for research purposes only and any problem or symptom should also be reported to their transplant physician or nurse.

9.2 Protection Against Risks

Risks of physical performance testing will be minimized by providing careful supervision with contact guard posture assistance to provide stability. Patients will be instructed to report any symptoms of fatigue, shortness of breath or chest discomfort, immediately prompting discontinuation of activity and appropriate medical management. Assessments will be carried out in 4 Oncology (inpatient medical oncology) units, infusion clinic, or oncology clinic with full and immediate medical response capacity available. The activity intervention will take place in the hospital in the presence of trained personnel to minimize risks. Patients will receive careful instruction on the activity technique, and each session will be tailored to the individual's level of functioning, symptoms and confidence. Prior to approaching each patient on a daily basis, the interventionist will review a checklist with the patient's nurse to identify any medical contraindications to participation. In addition, the participants supervising attending oncologist will confirm medical eligibility of each subject prior to enrollment on study.

Confidentiality of data is maintained by using research identification numbers that uniquely identify each patient. Appropriate measures are taken to prevent unauthorized use of study information. The research ID number will be used. Any paper research records will be kept in a

locked cabinet in the study coordinator's office. The files matching participants' names and demographic information with research ID numbers will be kept separately in a password protected data file. Only selected study personnel will have access to these files. After the study is completed, paper records will be stored with other completed research studies in a secured storage vault. Data will be used only in aggregate and no identifying characteristics of individuals will be published or presented.

9.2.1 Patient Confidentiality

We do not anticipate any breach of confidentiality as no records will be shared with any personnel outside the clinicians caring for the patients and the research team. Any information about participants obtained from this research will be kept as confidential as possible. All data obtained either through: Lineberger PRO-Core software, patient chart review, or by direct patient contact will be stored with a study ID rather than patient identifiers. A list of patient names and their study IDs will be kept in a locked cabinet. Electronic data will be de-identified and stored on a secure server.

9.3 Unanticipated Problems

9.3.1 Definition

As defined by UNC's IRB, unanticipated problems involving risks to study subjects refers to any incident, experience, or outcome that:

- Is unexpected (in terms of nature, severity, or frequency) given (a) the research procedures that are described in the protocol-related documents, such as the IRB-approved research protocol and informed consent document; and (b) the characteristics of the subject population being studied;
- Is related or possibly related to a subject's participation in the research; and

Suggests that the research places subjects or others at a greater risk of harm (including physical, psychological, economic, or social harm) related to the research than was previously known or recognized.

9.4 Removal of Patients from Protocol

Patients will be removed from the study if they indicate they no longer wish to participate and if they are not able to complete the activity due to disease/treatment complications. Additionally, exclusions will occur if the oncologist requests that his/her patient is excluded from the study for medical or emotional concerns.

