5.3.2 PRO-CTCAE (daily measures)

This 78-item measure, developed at the National Cancer Institute (NCI) allows patients to self-report symptom-based adverse events. We will use a subset of 19 symptoms to assess symptom attributes (e.g., presence, frequency, severity, interference with symptom) deemed relevant for cancer patients; these symptom-items have been extensively evaluated by cancer patients using cognitive interview³² methods and found to be clear, comprehensible, and capable of measuring the symptoms of interest and are most relevant for this population, such as nausea and vomiting. In our bone marrow transplant study (preliminary study 3, in which most of the patients had some type of leukemia, these items captured symptoms of fatigue, diarrhea, heartburn, nausea, appetite, anxiety, mouth sores, vomiting, pain, constipation, sadness, cheering-up, insomnia, cough, rash, and shortness of breath. In the proposed study, both the control and intervention groups will be asked to answer the 19 questions daily to capture changes over time. Recent data have shown that daily collection of patient-reported symptoms is feasible and acceptable to bone marrow transplant patients in the inpatient setting, who are often patients with AML.³³ We will calculate a total symptom score. This symptom score represents treatment-related symptom burden for that patient on that particular day.

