5.4 Duration of Study

Active participation by a given subject will be complete approximately 6 months after cycles 1, 2, 3, and 4 based on participants' treatment schedule. Ongoing data collection through medical record abstraction will continue for collection of use of UNC services.

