Analyses will be conducted following an intention to treat approach, such that patients are analyzed as allocated. Descriptive statistics will be computed on all analysis variables at each time point separately for each condition. These values will be compared between the conditions at baseline to determine whether any imbalanced. These include means and standard deviations for continuous variables, and frequencies and percentages for categorical variables. As the primary analysis of pre and post values, we will fit an analysis of covariance (ANCOVA) model for each post outcome, with a main effect for group (intervention versus control) while controlling for the covariate of the corresponding baseline (pre) value. Sensitivity analyses will repeat this ANCOVA but adding demographic variables that are imbalanced at baseline, subject to sufficient sample size. This approach will allow us to assess whether the mean post values differ between groups for each measure through the regression coefficient for the main effect of group, as well as its 95% confidence interval. This information will be useful in planning for the subsequent R01, and we will calculate effect sizes for the post measure as the ratio of the mean difference between the intervention and the control groups to its standard deviation. For measures where more than one follow-up measure is collected, this approach can be extended through a linear mixed effects model approach to repeated measures analysis, and within-patient correlation can be estimated. If extensive (e.g., greater than 10%), multiple imputation will be considered for missing values. No formal significance testing will occur, as the intention is to evaluate and estimate effect sizes rather than formal hypothesis testing, and hence multiplicity is not a concern from this perspective.

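### Section 9.4 takes patients out of the study when complications stop an undefined activity, and no outcome assessment is provided for afterwards, which undercuts analysis as allocated

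*Combined protocol and SAP*

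**What the plan says.** **Removal.** Section 9.4 removes from the study patients who no longer wish to participate "and if they are not able to complete the activity due to disease/treatment complications". A second sentence lets the oncologist have a patient taken off for medical or emotional concerns.

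**The activity.** The term is not defined. Section 9.2 uses the word in two senses. Symptoms during physical performance testing are to be reported, "immediately prompting discontinuation of activity and appropriate medical management". The same section then speaks of an activity intervention delivered in hospital by trained personnel, which is PACT.

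**After removal.** Section 5.4 says: "Ongoing data collection through medical record abstraction will continue for collection of use of UNC services". Section 5.1 allows contact for up to 2 years from diagnosis. Section 10.3 records attrition and its reasons. None of these schedules an assessment.

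**Analysis.** Section 10.3 states: "Analyses will be conducted following an intention to treat approach, such that patients are analyzed as allocated". Each post outcome is modelled by ANCOVA on its baseline value. A mixed model is an option where there is more than one follow-up. On missing data: "If extensive (e.g., greater than 10%), multiple imputation will be considered for missing values".

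**Scheduled outcomes.** In section 5.3.2, "both the control and intervention groups will be asked to answer the 19 questions daily to capture changes over time". In Table 5 (section 8.0), the QLQ-C30, FACT-Leu, PActS and KPS are marked under "Baseline cycles 1 & 2 (7 days prior or within 3 days of infusion initiation" and again under "Before cycle 4 (About day 90". The QLQ-C30 also has a mark at the baseline of cycle 3, and the KPS one at the end of infusion in cycles 1 and 2. PASS, grip strength, Berg, Timed Up and Go and AM-PAC are marked only in the baseline column.

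**The concern.** Stopping an activity and leaving the study are different events, and section 9.4 merges them. A patient whose complications end the activity has no scheduled assessment from then on, so has no later QLQ-C30, PRO-CTCAE, FACT-Leu, PActS or KPS value. An ANCOVA on observed post values drops that patient, whatever the allocation.

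The patients lost this way are likely to have the worst later values. Section 1.2 says that this population has cumulative fatigue and functional decline and is often admitted with complications, so the trigger is realistic. Controls receive usual care (section 2.0). If the activity is PACT activity, the rule therefore acts mainly on one arm, and the effect sizes meant to plan the subsequent R01 would probably be too favourable. If it is performance testing, the comparison is roughly balanced, but both arms then describe only patients well enough to continue.

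Retention is affected as well. Section 3.4.1 counts patients who completed the intervention, and section 10.3 counts those without attrition from the study. Removal lowers both. It ends the nurse's symptom review and the twice-weekly calls on days 8-30 and 38-60 (Table 1), which a patient unable to do the activity might still have completed.

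**Working it through.** **1. Does any section supply outcomes after removal?** Sections 5.1, 5.4, 5.5 and 10.3 come closest. They give permission to contact, chart data, and the reasons for attrition. None gives a QOL, symptom or function assessment.

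**2. Which wording applies?** Read literally, the *and if* in section 9.4 needs both a wish to stop and inability. The clause would then add nothing to withdrawal. Two separate triggers is the likelier intent and is assumed below.

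**3. The plan's precision figure.** Section 10.2 gives a 95% half-width of 0.9 SD with 10 per group. Normal: 1.96 × √(2/10) = 0.877. t with 18 df: 2.101 × √(2/10) = 0.940. Both round to 0.9, so the figure reproduces.

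**4. Possible size of the bias.** Apart from the 12 per group in section 10.2, every input is an assumption:

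- no true effect, and unit-variance normal variables with high values good
- r = correlation of baseline with post
- ρ = correlation of health status with post
- s = correlation of health status with baseline
- the k sickest patients are removed

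Dropping the 2 lowest of 12 standard normal values (expected −1.629 and −1.116) shifts the mean of the other 10 by d = 2.745/10 = 0.274. Post rises by ρd and baseline by sd, and ANCOVA takes back r × sd. So

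bias ≈ (ρ − r·s) × d.

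With r = 0.5, 2 of 12 PACT patients removed and no controls:

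| Case | ρ | s | Formula | Simulated (40,000 trials) |
|---|---|---|---|---|
| Low | 0.3 | 0.7 | (0.3 − 0.35) × 0.274 = −0.014 | −0.016 |
| Middle | 0.5 | 0.25 | (0.5 − 0.125) × 0.274 = 0.103 | 0.10 |
| High | 1 | 0.5 | (1 − 0.25) × 0.274 = 0.206 | 0.21 |

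Positive values favour PACT.

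**5. Sensitivity.**

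- One control also removed: the control shift is 1.629/11 = 0.148, so d becomes 0.274 − 0.148 = 0.126. Middle case 0.375 × 0.126 = 0.047; high case 0.75 × 0.126 = 0.095. Both are about half.
- Two removed from each arm: between-arm bias about 0, but each arm's mean looks 0.08 to 0.28 SD better.
- One PACT removal: about 0 to 0.11. Three: about 0 to 0.31. None: 0.
- Two PACT removals with r = 0.3: 0.03 to 0.25. With r = 0.7: −0.06 to 0.15.

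**6. Would imputation repair it?** In the middle case, regression imputation from baseline alone leaves 0.11 against 0.10, so nothing is gained. Table 5's first column may give a cycle 2 value for some questionnaires. An interim value with assumed correlation 0.7 with post cuts the bias to 0.05 to 0.07.

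**The case against.** **Missing data do not contradict analysis as allocated.** This is fair. A reader might infer that sections 9.4 and 10.3 are in outright contradiction. They are not: a patient with no post value can still be counted in the allocated arm. The rule undercuts the principle because it creates the missing values.

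**The plan has remedies.** Section 10.2 already expects 20% of values to be missing, which is above the 10% example for imputation. The optional mixed model would keep earlier follow-up values, including daily PRO-CTCAE, in the allocated arm. This stands in part. Both remedies are optional, and both normally assume data missing at random, which is doubtful when complications cause the loss.

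**Loss from PACT alone is the extreme case.** This stands. The oncologist route in section 9.4 covers both arms, and one control loss against two PACT losses halves the bias. The 20% in section 10.2 is also the same for both groups.

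**Few patients may qualify.** Section 9.2 tailors sessions and checks for contraindications daily. This stands, and it is one reason why the size is unknown.

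**Much of the function data is unaffected.** This stands for the five measures that Table 5 marks only in the baseline column. For them, the table schedules nothing later whether or not a patient is removed.

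**This is a small, sequential, non-randomised pilot** with feasibility as primary endpoint and no formal testing of these outcomes. That lowers the stakes, but section 10.3 intends the estimates for planning the R01, and this error would be systematic.

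A reader might also set section 7.0 against section 9.4, since it keeps patients who cannot undergo activity monitoring in the study. It concerns different patients, so it is a precedent and not a conflict.

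**Conclusion.** The point holds as a gap worth closing. Section 9.4 ends study participation when complications stop an undefined activity, and no section provides for outcome assessment afterwards. Followed as written, it loses later QLQ-C30, PRO-CTCAE, FACT-Leu, PActS and KPS values in the sickest patients, and it can lower retention under both definitions.

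A reader might go further and infer that the plan's comparison is biased toward PACT. The documents do not support that as a flat statement. The direction depends on reading the activity as PACT activity, and the size cannot be derived from the documents. Under the assumed inputs above it is about 0 to 0.21 SD with 2 of 12 PACT patients and no controls removed, 0.10 SD in the middle case, and about half that if one control also leaves. Under the performance-testing reading, between-arm bias is about 0. All of these values lie inside the 0.9 SD half-width, so the fault does not invalidate the pilot.

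**What to change.** - In section 9.4, clarify *and if* and define the activity.
- Separate stopping the activity from leaving the study. In both arms, keep collecting the Table 5 questionnaires and chart data already scheduled, unless the patient withdraws or leaves at the oncologist's request under the existing rule. Analyse as allocated.
- Report *stopped activity* and *left study* separately, by arm and reason, and reconcile section 9.4 with section 10.3. Say which of the two events counts against retention in sections 3.4.1 and 10.3.

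Who stops the activity, and when, is left to the investigators.

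**Cost.** A few sentences, plus continued collection of assessments already on the schedule. Some assessments in ill patients will still be missed, so only part of the bias goes. If half of the removed patients could be assessed, the middle case would fall from 0.10 to 0.05 SD and the high case from 0.21 to 0.10 SD.
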